Data Analysis	
STATISTICAL ANALYSES
 
The detailed methodology for conduct of the statistical analysis of data collected in the setting of this study will be documented in a Statistical Analysis Plan (SAP).
 
Tofacitinib maintenance will be estimated by considering the date of initiation of treatment with Tofacitinib and the date of permanent discontinuation. The time of follow-up of patients not presenting with an event of interest (permanent discontinuation of treatment) will be censored at the date of the last visit. Drug survival with Tofacitinib will be described using the Kaplan-Meier method in a full analysis set.
 
Principal analysis
 
Factors predictive of drug survival will be investigated using a Cox model. A univariate analysis will first be conducted. All potential factors for which the p-value resulting from the univariate analysis is strictly less than 10% will be included in a multivariate Cox model. Predictive factors and their interactions will be selected according to a backward (step-down) selection method. Predictive factors retained in the model will be those with a p-value < 5%.
 
Key secondary analysis
 
The impact of behavioural strategies (catastrophisation and coping) on Tofacitinib drug survival will be evaluated in patients suffering from RA. A Cox proportional hazards model will be used with the 5 dimensions of the coping questionnaire and the catastrophisation score collected at the baseline visit included as independent variables.

Effectif	300 patients
Regulatory	RIPH de catégorie 3 CNIL : Méthodologie de référence MR003

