First, the effect of each factor on drug survival will be tested with a univariate Cox model. Thus, the hazard-ratios calculated are called “raw”. They will be presented with their 95% confidence interval and their associated p-value. Then, all potential factors for which the p-value resulting from univariate analysis is strictly less than 10% will be included in a multivariate Cox model. Predictive factors and their interactions will be chosen using a backward (step-down) selection. Predictive factors chosen will be those which have a p-value < 5%. In the case of a significant interaction, all individual components of the interaction will be “forced” in the model, whether they are statistically significant or not. The adjusted hazards-ratios thus obtained will be presented with their 95% confidence interval and their associated p-value.

Missing data will be managed using a method based on missing data indicators^(50, 51). This method is not a method of imputation of missing data. A fixed value will be assigned to missing observations, and a dummy variable (1/0) will be added to the multivariate model in order to indicate if the value of this variable is missing or not. If more than 10% of the patients have missing baseline covariates, a complete case analysis will also be performed as a sensitivity analysis. Additional methods for handling missing data may also be used. Further details will be provided in the statistical analysis plan as appropriate.

Secondary analyses

The impact of behavioural strategies (catastrophisation and coping) on Tofacitinib drug survival will be evaluated in patients suffering from RA. A Cox proportional hazards model will be used with the 5 dimensions in the coping questionnaire and the catastrophisation score collected at the baseline visit included as independent variables.

In a second phase and in a similar manner, a Cox model will be used to estimate the impact of the adaptive strategies under treatment. Therefore, the last evaluation available before discontinuation of treatment (or the last visit if a patient does not permanently discontinue treatment) and the change between this latter evaluation and the baseline value will be taken into account in separate models.

The correlation between behavioural strategies and effectiveness will be studied with Pearson's or Spearman's coefficient according to the nature of variables compared.

Interim analysis

Interim descriptive analyses will be conducted annually.

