2.4 STUDY OBJECTIVES

The primary objective of this study is to identify factors predictive of drug survival with Tofacitinib in RA patients. To assess this the time (in days) which a patient is being treated with Tofacitinib, up to permanent discontinuation, will be modelled using Cox proportional hazard (PH) models and predictive factors will be investigated to assess their impact on the models.

The secondary objectives are:

- *To evaluate the impact of behavioural strategies in patients with rheumatoid arthritis on Tofacitinib drug survival* by including the PCS (total score) and CSQ (5 domain scores) in a Cox PH model
- *To study the correlation* (by considering relevant correlation coefficients) *between behavioural strategies and effectiveness*
- *To evaluate the effectiveness of Tofacitinib*
- *To evaluate the tolerability of Tofacitinib*

Unless specified otherwise, secondary endpoints will be assessed using summaries only.

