4 HYPOTHESES AND DECISION RULES

The primary and secondary analyses will use predictive models, described in Section 8.2.3 and Section 8.2.5.1, to assess Tofacitinib drug survival. All other summaries will analyse data descriptively.

There are no formal statistical hypotheses for this study.

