8.1.1 Analysis of Time to Event Data

8.1.1.1 Cox Proportional Hazards

Cox proportional hazards (PH) models will be used to analyse time to event data, where the event of interest is duration of Tofacitinib drug survival described in Section **Error! Reference source not found.** If a patient is not recorded as having permanently discontinued Tofacitinib, which is the event of interest, then they will have their time of follow-up censored at the date of their last visit.

For the primary analysis, univariate Cox PH models will be created for all of the potential predictive factors, see [Figure 2](#) in Section [8.2.3](#), that is a separate Cox PH model will be created for each factor. If the variable significantly impacts Tofacitinib drug survival at the 10% level then the factor will be put forward into a multivariate model.

Once the univariate model selection is complete, backwards selection will be used to remove factors from the multivariate model which do not have a significant p value at the 5% level. The covariate with the highest p value will be removed in turn until all factors have a p value less than 0.05. If a significant interaction is found then the individual factors of this interaction will be kept in the model, regardless of their p value. A significant interaction is tested for between all variables in the multivariate model.

Furthermore, for the primary analysis a table showing all of the 95% confidence intervals and p values for the “raw” hazard ratios coming from the univariate models will be created. This will be for all of the factors in [Figure 2](#), regardless of whether they’re included in the multivariate model.

For the secondary analysis, a multivariate Cox PH model will be created including the scores from the 5 domains of the CSQ at baseline and the total PCS score at baseline included as covariates.

A further two Cox PH models will be produced for the secondary analysis, for CSQ and PCS: the first including the last evaluation available before discontinuation (or last visit if

patient does not discontinue during the study) and the second including change from baseline to the last recorded measurement.

The SAS procedure PROC PHREG will be used to fit any Cox PH models and check the assumption of proportional hazards. If the assumption of proportional hazards is violated then alternative models will be considered.

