8.2.9 Summary of Analyses

Table 8 Summary of Main Analyses

Outcome	Analysis Set	Supports Protocol Objective Number	Subgroups	Statistical Method	Covariates/ Strata	Missing Data
Time to discontinuation of Tofacitinib	Full Analysis Set (FAS)	1	None	Cox PH model	Univariate model selection, followed by backwards selection on the variables in Figure 2 .	Missing data indicators
Sensitivity Analysis – Only to be used in the event of >10% missing data: Time to discontinuation of Tofacitinib	FAS	1 – Sensitivity Analysis	None	Cox PH model	Univariate model selection, followed by backwards selection on the variables in Figure 2 .	Complete Case Analysis
Sensitivity Analysis: Time to discontinuation of Tofacitinib	FAS	1 – Sensitivity Analysis	None	Random Survival Forests	Variables in Figure 2 , following methods seen in Section 8.1.1.2 Random Survival Forests .	Random Survival Forests missing data algorithm.
Sensitivity Analysis: Time to discontinuation of Tofacitinib	Month 3 Analysis Set	1 – Sensitivity Analysis	None	Cox PH model	Univariate model selection, followed by backwards selection on the variables in Figure 2 and Das28-4 CRP at Baseline.	Missing data indicators
Sensitivity Analysis: Time to discontinuation of Tofacitinib	Month 3 Analysis Set	1 – Sensitivity Analysis	None	Random Survival Forests	Variables in Figure 2 and DAS28-4 CRP at Month 3, following the methods seen in Section 8.1.1.2 Random Survival Forests .	Random Survival Forests missing data algorithm.
Time to discontinuation of Tofacitinib	FAS	2	None	Cox PH model	Baseline CSQ and baseline PCS	No missing data methods used.
Time to discontinuation of Tofacitinib	FAS	2	None	Cox PH model	Last recorded CSQ and PCS before discontinuation.	No missing data methods used.
Time to discontinuation of Tofacitinib	FAS	2	None	Cox PH model	Change from baseline to last recorded CSQ and PCS before discontinuation.	No missing data methods used.

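### Two of the three secondary PCS/CSQ Cox models use a score read at a time the outcome sets, so a trend shared by all patients can pass for an effect on drug survival

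*SAP*

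**What the plan says.** The secondary objective on behavioural strategies and drug survival is to be met "by including the PCS (total score) and CSQ (5 domain scores) in a Cox PH model" (SAP 2.4). SAP 8.1.1.1 turns this into three Cox models of time to permanent discontinuation:

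- **Baseline model:** baseline PCS total and the five baseline CSQ domains. The Protocol summary presents this as the key secondary analysis, with "the catastrophisation score collected at the baseline visit included as independent variables".
- **Last-value model:** "the first including the last evaluation available before discontinuation", or the last visit for a patient who does not stop.
- **Change model:** listed in SAP Table 8 (8.2.9) as "Change from baseline to last recorded CSQ and PCS before discontinuation".

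Protocol 9.7 introduces the last two with "In a second phase and in a similar manner, a Cox model will be used" and gives the same rule for the score. The clock starts at first dose, and patients without the event are censored at their last visit (SAP 6.1.1.1). SAP 8.2.6 limits these analyses to assessments made before permanent discontinuation. The one relevant model check is for proportional hazards: "If the assumption of proportional hazards is violated then alternative models will be considered". Neither document mentions a time-dependent covariate, a landmark or an adjustment for when the score was measured.

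**The concern.** A covariate held fixed from time zero should be known at time zero. Here it is read later, at a moment the outcome chooses: early for early stoppers, near month 24 for those who stay on drug. If catastrophising scores drift down in everyone, early stoppers show higher last scores and smaller improvements only because they were read sooner. A shared rise would bias in the opposite direction.

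The two provisions already in the SAP do not remove this. The on-treatment rule itself ends each stopper's data at stopping. The proportional-hazards check leads to no named model and, as shown below, seldom reacts to a steady trend.

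These two models are the only planned evidence on how behavioural strategies during treatment relate to drug survival. They will be reported with hazard ratios, confidence intervals and p-values, without multiplicity adjustment. Change from baseline in PCS and in CSQ is itself a listed secondary endpoint, so the study expects that these scores may move.

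**Working it through.** **1. The plan's own figure.** Protocol 9.5: N = 10k/p, with k = 50 × 0.3 = 15 and p = 0.50. This gives 150 events and 150/0.50 = 300 patients, as stated. (SAP 2.1 still says 500; 300 is used here.)

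**2. When the score is read.** Assume constant hazard, so S(t) = 0.5^(t/731), with the SAP target days. Expected stops are 300 × [S(a) − S(b)].

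| Stop between days | Expected stops | Last scheduled post-baseline value (day) |
|---|---|---|
| 0–30 | 8.4 | none |
| 30–91 | 16.4 | 30 |
| 91–183 | 23.0 | 91 |
| 183–365 | 40.0 | 183 |
| 365–548 | 33.8 | 365 |
| 548–731 | 28.4 | 548 |

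Stoppers with a post-baseline value: 150 − 8.4 = 141.6. Weighting the last column by the stops gives mean day 267, against day 731 for the 150 completing continuers. With 30% loss to follow-up the days are 250 and 553.

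A 4-point linear fall over 24 months, identical in everyone, amounts to 4 × 267/731 = 1.5 points at day 267 and 4 points at day 731. The groups differ by about 2.5 points with no link to stopping.

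**3. How often this gives a false finding.** Simulated cohorts of 300 had hazard ln2/731 per day, scores at the scheduled visits and scores independent of stopping. Models had six covariates, with 1,000 runs per scenario. Assumptions not in the documents: total SD 12, visit-error SD 6 or 8, pairwise correlation 0.2 or 0.5, loss 0 or 30%, and CSQ drift in the same SD units (4 points = 0.33 SD). Entries are rejection rates for PCS at nominal 5%.

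| Shared trend | Change model | Last-value model |
|---|---|---|
| None | 5% | 4–6% |
| Slow 4-point fall, all six scores equally | 7–23% | 7–16% |
| Slow 4-point fall, CSQ drifts half as much | 24–54% | 23–35% |
| Slow 4-point fall, PCS and CSQ Catastrophising only* | 24–44% | 16–26% |
| Slow 4-point fall, PCS only | 47–95% | 43–72% |
| 2-point fall complete by month 6* | 5–11% | 5–9% |
| 4-point fall complete by month 6* | 4–26% | 6–15% |
| 8-point fall complete by month 6* | 7–69% | 5–41% |

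*Error SD 6, no loss. The month-6 rows pool repeat runs of 500–600.

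Under equal drift the single-score rate is diluted across six covariates, but the joint six-score test rejects in 37–96% (change) and 33–73% (last value). In the change model with a slow fall, the hazard ratio per 10 PCS points is 1.04–1.60 when the truth is 1.00. Repeat simulations gave 4–8% with no trend and about 4–8% for the baseline model throughout.

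**4. Does the proportional-hazards check catch it?** A Grambsch–Therneau test on the PCS coefficient flags the slow fall in 5–15% (change) and 5–11% (last value) of runs. For falls complete by month 6 it flags 20–26% and 11–14% at 4 points, and 64–70% and 38–43% at 8 points.

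**5. With time-dependent covariates.** Six-covariate models under the slow fall, with and without loss: PCS 4.9–5.9%, joint test 5.2–6.1%, hazard ratio 0.998–1.004.

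**6. A separate, conditional point.** The Month 3 Analysis Set (SAP 5.3) does not require patients to be on tofacitinib when measured, and follow-up continues after stopping. Expected stops before day d are 300 × (1 − 0.5^(d/731)): 24.8 at day 91, and 17.1 to 36.5 across the window of days 62–137. The month-3 DAS28-4 CRP analyses are biased only if such patients are measured and their DAS28 differs after stopping. Table 8 also gives that Cox model DAS28-4 CRP at baseline, where SAP 8.2.4 says month 3.

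**The case against.** **The weight is limited.** The two models are a second phase of a secondary objective, the key secondary analysis uses baseline scores, and SAP 4 states that "There are no formal statistical hypotheses for this study". This stands. It limits how much rests on the result but does not make the estimate right.

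**The size is unknown.** No trend, SD or correlation is given, and the rates run from nominal to 95%. The highest need a 24-month fall in PCS while every CSQ domain, including Catastrophising, stays flat. An early 2-point fall, or an early 4-point fall shared equally, stays near nominal. This stands: the mechanism is certain, its size here is not.

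**The proportional-hazards check may warn.** It does so often for a large early fall, but rarely for a steady one. A warning leads only to unspecified alternatives.

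**Sites should add a visit at discontinuation.** If that value is used, the mean reading day for stoppers moves to about 324, still far from 731. In a PCS-only model with a slow fall (SD 6, no loss) the false-positive rate drops only from 78.8% to 70.0%.

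**Simpler remedies exist.** A month-3 landmark model also held its level (3.5–7%) and is acceptable, though it answers a narrower question. Labelling the models descriptive would lower the claim but leave the biased hazard ratio in place.

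**Conclusion.** The concern holds. The last-value and change models are wrong as written whenever PCS or CSQ scores trend during treatment, because the time of reading depends on the outcome. The timing gap (mean day 267 against 731) rests on the plan's 50% survival plus a constant hazard. The error rates are illustrations under assumed SDs, correlations and trend shapes: from about nominal for small early falls to well above half for a slow fall confined to PCS. With no trend there is no bias. The primary analysis and the baseline PCS/CSQ model are untouched. This should be corrected before analysis, but it does not threaten the main result. The month-3 point is conditional and the Table 8 entry clerical; neither adds to the weight of the main point.

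**What to change.** 1. Replace the two models with counting-process Cox models in PROC PHREG, entering the most recent PCS total and five CSQ domain scores, or their changes from baseline, as time-dependent covariates. Use only values from visits before the event and leave out the visit triggered by discontinuation. The on-treatment rule already drops that visit if it is dated after stopping, but not if it is dated before. Identify it by date and visit type, since the Table 9 windows would relabel it as a scheduled visit. Start risk time in the change model at the first post-baseline visit. Keep the baseline model, and record the change in SAP 1.2.
2. Run the month-3 DAS28-4 CRP analyses as landmark analyses from the actual measurement date, in patients then still on tofacitinib and under follow-up.
3. Reconcile Table 8 with SAP 8.2.4 on month 3.

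**Cost:** SAP wording and modest programming, with no new data. Protocol 9.7 allows the SAP to alter its plans, and the primary endpoint does not change. About 8 of 150 events (stops before the first post-baseline visit) leave the change model. The hazard ratio takes a new meaning: it describes the current score, carried forward for up to 6 months between visits. The landmark drops about 25 of 300 patients if month 3 is measured at day 91 and all early stoppers would otherwise have been measured.

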8.1.1.2 Random Survival Forests

Random survival forests will be produced as part of the sensitivity analyses, and will analyse time to Tofacitinib discontinuation. It will consider all of the potential factors seen in [Figure 2](#) in Section [8.2.3](#). The program R will be used for this, using the package 'randomForestSRC'. For survival data, this package uses splits with either the default rule as log-rank splitting [\(9, 7\)](#) or log-rank score splitting [\(8\)](#). We will primarily use the default but a further sensitivity analysis, will also be performed using the log-rank score splitting and compared with the results when using log-rank splitting.

Suggested steps of random survival forests are as follows [\(6\)](#):

1. Draw ntree (1500 in our case) bootstrap samples from the original data. (Each bootstrap excludes a percentage of the data called out-of-bag (OOB) data which will be used for testing accuracy)
2. Grow a tree for each bootstrapped data set. At each node of the tree randomly select mtry predictors (covariates) for splitting on. Split on a predictor using a survival splitting criterion. A node is split on that predictor which maximizes survival differences across daughter nodes. We will use cross validation to determine the best mtry.
3. Grow the tree to full size under the constraint that a terminal node should have no less than nodesize unique failures.

4. Calculate an ensemble cumulative hazard estimate by combining information from the ntree trees. One estimate for each individual in the data is calculated.

5. Compute an OOB error rate for the ensemble derived using the first b trees, where b = 1, . . . , ntree. Estimate the prediction error for the ensemble cumulative hazard function.

Variable importance will also be compiled and presented in an output.

Ensemble estimation

The randomForestSRC package produces an ensemble estimate for the cumulative hazard function and this will be presented in a table. Error rate performance is calculated based on this value, which will also be presented.

8.1.2 Correlation Analysis

The correlation between behavioural strategies (measured by PCS total score and 5 domains of the CSQ) and effectiveness will be studied with Pearson's or Spearman's coefficient according to the nature of variables compared. This will be calculated for all effectiveness endpoints. To investigate the relationship between a categorical variable and a continuous variable, boxplots for each category will be produced and a visual comparison will be made (there will be no correlation co-efficient for these comparisons).

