8. STUDY OBJECTIVES

Primary objective of the study

- To identify factors predictive of drug survival with Tofacitinib

Secondary objectives

- To evaluate the impact of behavioural strategies in patient with rheumatoid arthritis on Tofacitinib drug survival
- To study the correlation between behavioural strategies and effectiveness
- To evaluate the effectiveness of Tofacitinib
- To evaluate the tolerability of Tofacitinib

[figure not shown]

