6.1.1.2.10 DAS28 (EULAR Criteria)

The DAS28 EULAR criteria to evaluate patient response to treatment is categorised by good responder patient, moderate responder patient, non-responder patient and non-evaluable patient based on patients DAS28-4 CRP score and the decrease in DAS28-4 CRP compared to Visit 0. [Table 3](#) below gives further detail of the categorisation.

Table 3 Evaluation of patient response to treatment using DAS28 (EULAR Criteria)

DAS28 at visit	Decrease in DAS28 compared to V0		
	>1.2	>0.6 and ≤1.2	≤0.6
≤3.2	Good responder	Moderate responder	Non-responder
>3.2 and ≤5.1	Moderate responder	Moderate responder	Non-responder
>5.1	Moderate responder	Non-responder	Non-responder

The DAS-28 EULAR Criteria will also be derived based on the DAS28-4 ESR score using the same approach as above.

The individual components of DAS28-4 CRP and DAS28-4 ESR, which are the composite endpoints used in this criteria, are collected at all visits (Inclusion visit, V1, V2, V3, V4, V5, V6 and any additional visits in the case of discontinuation of Tofacitinib).

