8.2.6.1 Behavioural Strategies – PCS and CSQ

The impact of behavioural strategies (PCS total score and 5 domains of the CSQ) on Tofacitinib drug survival will be analysed, using three multivariate Cox PH models as described in Section 8.1.1.1 Cox Proportional Hazards.

PCS (individual domain scores and total scores) and CSQ (individual domain scores) will also be summarised as continuous variables as per Section **Error! Reference source not found.** PCS total score will also be summarised as a dichotomous variable (<20 vs ≥ 20) as per Section **Error! Reference source not found.**

Correlations between the behavioural strategies (PCS total score and 5 domains of the CSQ) and each of the endpoints listed below will be investigated as outlined in Section **Error! Reference source not found.**, for the endpoints seen in Figure 3:

- DAS28-4 ESR
- DAS28-4 CRP
- TJC
- SJC
- Duration of morning stiffness
- GIRERD Questionnaire
- EuroQoL EQ-5D-3L
- SF-12v2 Questionnaire
- FACIT-Fatigue Questionnaire
- DAS28 (EULAR Criteria)
- Pain

Figure 3 Timepoints for correlation analyses

Behavioural Strategies Timepoint	Effectiveness Endpoint Timepoint
M0 (Baseline)	M3
M0 (Baseline)	CFB to M3 (M3-M0)
M3	M3
M3	CFB to M3 (M3-M0)
CFB to M3 (M3-M0)	M3
CFB to M3 (M3-M0)	CFB to M3 (M3-M0)
M0 (Baseline)	M6
M0 (Baseline)	CFB to M6 (M6-M0)
M6	M6
M6	CFB to M6 (M6-M0)
CFB to M6 (M6-M0)	M6
CFB to M6 (M6-M0)	CFB to M6 (M6-M0)
M0 (Baseline)	M12
M0 (Baseline)	CFB to M12 (M12-M0)
M12	M12
M12	CFB to M12 (M12-M0)
CFB to M12 (M12-M0)	M12
CFB to M12 (M12-M0)	CFB to M12 (M12-M0)
M0 (Baseline)	M24
M0 (Baseline)	CFB to M24 (M24-M0)
M24	M24
M24	CFB to M24 (M24-M0)
CFB to M24 (M24-M0)	M24
CFB to M24 (M24-M0)	CFB to M24 (M24-M0)

M = Month. CFB = Change from baseline.

Logistic regression will be considered to assess the relationship between behavioural strategies (PCS total score and 5 domains of the CSQ) and each of the binary endpoints listed below as outlined in Section **Error! Reference source not found.**, with a separate model created for each of the timepoints seen in Figure 4:

- LDA
- Patients in remission
- FiRST Questionnaire

Figure 4 Timepoints for logistic regression

Behavioural Strategies Timepoint	Effectiveness Endpoint Timepoint
M0 (Baseline)	M3
M3	M3
CFB to M3 (M3–M0)	M3
M0 (Baseline)	M6
M6	M6
CFB to M6 (M6–M0)	M6
M0 (Baseline)	M12
M12	M12
CFB to M12 (M12–M0)	M12
M0 (Baseline)	M24
M24	M24
CFB to M24 (M24–M0)	M24

M = Month. CFB = Change from baseline.

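### EULAR response is listed for correlation with behavioural strategies, but the SAP gives it only boxplots and no estimate of association; separately, 12 of its 24 planned time-point rows are undefined.

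*SAP*

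**What the plan says.** The secondary objective in protocol section 8 is "To study the correlation between behavioural strategies and effectiveness". Protocol 9.7 gives the method: "The correlation between behavioural strategies and effectiveness will be studied with Pearson's or Spearman's coefficient", the choice depending on the type of variable. SAP 2.4 likewise says that correlation coefficients will serve this objective.

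SAP 8.1.2 repeats the protocol method and adds: "This will be calculated for all effectiveness endpoints". It then makes an exception for a categorical variable against a continuous one: "boxplots for each category will be produced and a visual comparison will be made", and "there will be no correlation co-efficient for these comparisons".

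SAP 8.2.6.1 applies this section: "Correlations between the behavioural strategies (PCS total score and 5 domains of the CSQ) and each of the endpoints listed below will be investigated". The list includes the entry beginning "DAS28 (EULAR Criteria", and the time points are those of Figure 3. SAP 8.2.6.3 classes EULAR response as categorical, together with GIRERD. SAP 6.1.1.2.10 builds it from DAS28 at the visit and "the decrease in DAS28-4 CRP compared to Visit 0", with an ESR version derived in the same way.

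Logistic regression (SAP 8.1.3 and 8.2.6.1, Figure 4) covers low disease activity, remission and FiRST. EULAR response is not among them.

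**The concern.** The SAP promises a correlation for EULAR response, a protocol secondary endpoint in its own right, and then withholds the statistic. The reader of the report would get plots of each behaviour score by response category, with nothing to say how strong an association is or how uncertain. Good, moderate and non-response are ordered, so a rank or ordinal method is available. The reason for leaving out an estimate is not given.

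The second problem is one of definition. Figure 3 is a single grid applied to every endpoint in the list. Half its rows ask for change from baseline in the endpoint, and EULAR response has no usable baseline value. A programmer would have to skip those rows or invent a rule.

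**Working it through.** The documents give no figure for this analysis, so there is none to reproduce. The check is a trace of the planned analyses, a count of Figure 3 rows, and Table 3 of the SAP applied at V0.

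**1. Which planned analyses link EULAR response to PCS or CSQ?**
- Correlation (8.1.2, 8.2.6.1): listed, but categorical against continuous, so boxplots only.
- Logistic regression (8.1.3, 8.2.6.1): not listed.
- Cox models (8.1.1.1, 8.2.6.1): the outcome is drug survival, not EULAR response.
- Categorical summaries (8.2.6.3): counts and percentages by visit, with no behaviour score.

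Planned coefficients, odds ratios, intervals or p-values for EULAR response against behaviour: 0.

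**2. Do the texts agree?** One sentence of 8.1.2 requires the coefficient for every effectiveness endpoint; a later one excludes categorical pairs. The specific exclusion presumably governs, but it then departs from SAP 2.4 and from protocol 9.7, which offers a choice between two coefficients and no third option. SAP 1.2, on amendments from the protocol, mentions only visit windows.

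**3. Figure 3 rows.** At each of months 3, 6, 12 and 24, three behaviour time points (baseline, visit, change) are crossed with two endpoint time points (visit, change).
- Rows: 4 × 3 × 2 = 24.
- Rows with change in the endpoint: 4 × 3 × 1 = 12, or 50%.
- Behaviour scores: 1 PCS total + 5 CSQ domains = 6.
- Comparisons per DAS28 version: 6 × 24 = 144, of which 6 × 12 = 72 need a change in EULAR response and 72 do not.

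**4. Is that change defined?** SAP 6.1 defines change from baseline as the visit value minus the baseline value. Categories cannot be subtracted. If Table 3 is nevertheless applied at V0, the decrease is 0, which falls in the ≤0.6 column, and every patient is a non-responder whatever the DAS28. A change from that constant would only restate the visit category. Figure 4, for the binary endpoints, has 4 × 3 = 12 rows and none with change on the endpoint side. Figure 3 was not adapted in this way for EULAR response.

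**5. What an estimate would add (illustration).** For Spearman's ρ, the interval is tanh(atanh ρ ± 1.96 × SE), with SE = √[(1 + ρ²/2)/(n − 3)]. Assume ρ = 0.20 and no missing data.
- n = 300 (protocol target, an upper limit): SE = √(1.02/297) = 0.0586; 95% CI 0.09 to 0.31.
- n = 150 (300 × the 50% drug survival at 24 months assumed in protocol 9.5, since 8.2.6.1 is analysed on treatment only): SE = √(1.02/147) = 0.0833; 95% CI 0.04 to 0.35.

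An interval running from almost nothing to a moderate association cannot be read off a boxplot.

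**The case against.** The strongest reply is that the information is largely recovered elsewhere. EULAR response is a recoding of two numbers, DAS28 at the visit and its decrease from V0. Both DAS28-4 CRP and DAS28-4 ESR are in the same correlation list, as visit value and as change, and both get coefficients. Low disease activity, whose DAS28 definitions use the 3.2 cut-off that also appears in Table 3, gets odds ratios with intervals and p-values. This stands, and it limits the impact. It does not explain why a separately listed endpoint has no estimate.

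A second reply is that the boxplot rule is an explicit choice in a descriptive plan. SAP section 4 has no formal hypotheses, SAP 2.4 defaults to summaries for secondary endpoints, and protocol 9.7 allows the SAP to modify its plans. This partly stands: the departure is permitted. But an estimate with an interval needs no hypothesis, and 8.1.2 contradicts itself whichever sentence is preferred.

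Four stronger readings are tempting and are not supported:
- *The secondary objective fails for treatment response.* It does not. The objective concerns effectiveness as a whole, and boxplots do show direction and rough size. What is missing is a formal estimate and its uncertainty.
- *The undefined rows cause the missing estimate.* They do not. The boxplot rule alone causes it, and deleting the rows would create no estimate.
- *The binary endpoints carry less information, so EULAR response deserves at least as much.* This is not generally true. Remission separates DAS28 below 2.6, whereas Table 3 pools everything up to 3.2. A patient at or below 3.2 with a decrease of at most 0.6 has low disease activity by DAS28 but is a EULAR non-responder.
- *There are 288 planned comparisons, 144 of them impossible.* This assumes that both DAS28 versions enter the correlations. SAP 6.1.1.2.10 derives both, but 8.2.6.1 lists the endpoint once and does not say.

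**Conclusion.** The point holds as a gap of limited consequence. No estimate of association between EULAR response and any of the six behaviour scores is planned, although the endpoint is listed for correlation and three places in the documents (8.1.2 itself, SAP 2.4, protocol 9.7) call for coefficients. As a separate defect, 72 of the 144 score-by-row comparisons per DAS28 version rest on a change that is undefined. The count follows from Figure 3 and the six scores and needs no assumption beyond one DAS28 version; the 50% share is the same if both are used. The precision figures depend on an assumed ρ and on assumed numbers of patients. The primary analysis is not affected.

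**What to change.** In the SAP, for EULAR response:

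1. Mark the 12 Figure 3 rows with endpoint change from baseline as not applicable.
2. For the other 12 rows, report an ordinal association (non, moderate, good) with each behaviour score and its 95% CI. Either a Spearman coefficient, which the plan already names, or an odds ratio from a proportional-odds model, which extends the logistic programs of 8.1.3, would do. Choose one in advance and keep the boxplots as illustration.
3. Exclude non-evaluable patients (the fourth category in 6.1.1.2.10) from these estimates and report their number by visit.
4. State whether the CRP version, the ESR version or both are used.
5. Reconcile the two sentences of 8.1.2. If the boxplot rule stays for any endpoint, list it in SAP 1.2 as a departure from the protocol. GIRERD falls under the same rule, so the revised wording should cover it too.

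The cost is SAP wording and a small amount of programming; no new data are needed. There are two downsides. The proportional-odds assumption must be checked if that model is used. The change also adds 6 × 12 = 72 exploratory estimates per DAS28 version (144 if both are used), with no multiplicity adjustment, so they should be labelled exploratory.
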